## 7.6 Return of Results

The designated laboratory will transfer participant genetic testing results to the EHR. Genetic results will be imported into the study database. Providers will be notified of participant results via standard site-specific laboratory return of results methods, a static report/consult note with interpretation and treatment recommendations, and, where possible, a CDS within the EHR as described in Sections 7.1 and 7.7.

After their participation in the trial is complete, the PGx testing results will be actively returned to the participants. The PGx testing results that are returned to the participant will follow current FDA guidance.

## 7.7 Clinical Decision Support Systems

Providers will be notified of participant results via standard site-specific laboratory return of results methods, a static report/consult note with both interpretation and treatment recommendations, and, where possible, a just in time alert within the electronic health system. Sites will work with their institutional information technology departments to set up provider alerts for actionable PGx phenotypes when a relevant opioid or SSRI medication is ordered. Provider alerts will indicate the participant's genetic results, the predicted phenotype (e.g. efficacy of various opioid or SSRIs), and prescribing recommendations.

Continuing on the health IT collaborative efforts established in IGNITE I through CDSKB (<http://cdskb.org>), all participating sites will seek to harmonize their CDS logic, recommendations, and provider alerts using a framework of required and optional elements for both the static report and the just in time alert. However, due to the pragmatic nature of the trial, the many involved research sites, and variations in local CDS policies, it is anticipated that there will be differences in CDS implementation details, but all sites will ensure that providers are alerted to the PGx test results and associated significance. Details of the alerts will be provided in the MOP.

## 7.8 Data Collection from the Electronic Health Record

Data collected from the local EHR will include prescription information and encounters including clinic visits, hospitalizations, and emergency department visits and associated diagnoses for the study interval time-zero through six-month follow up. Sites will extract data using prespecified programmatic algorithms, site-developed algorithms, and/or manual chart abstractions. EHR query results will be sent to the IGNITE PTN CC via secure data transfer and formatted for consistency across sites. Details for the EHR elements and transfer process will be provided in the MOP.

## 7.9 Data Collection from CMS and State Medicaid Agencies

Medicare and Medicaid claims data from CMS and state Medicaid agencies will be used to assess health care utilization, costs, and medications among participants covered by either Medicare or Medicaid. Claims made in the period of 12 months prior to surgery (acute pain) or return of results (chronic pain, depression) through 6 months following those events will be collected. See Section 9 and the MOP for additional details. Schedule of Activities and Timeframe for Collection of Endpoints

**Table 8. Data collection schedule**

### Data collection schedule, method of data collection, and timing

Outcome	Data source/instrument	Baseline	10 d ± 3 d	1 mo. ± 7 d	3 mo. ± 14 d	6 mo. ± 14 d
Pain Assessments						
Pain intensity	PROMIS Pain intensity scales	AP, CP	AP	AP, CP	AP, CP*	AP, CP
Pain intensity	PROMIS Numeric Rating Scale - Pain Intensity (NPRS)	AP	AP*	AP	AP	AP
Daily opioid dose & type of opioid use	Average daily mg morphine equivalents (MED) since discharge use of opioids: tramadol/ codeine vs others		AP*	AP		
Opioid use disorder	PROMIS - Prescription pain medication misuse subscale	AP, CP			AP, CP	AP, CP
Mobility	PROMIS mobility	AP	AP	AP	AP	AP
Depression Assessments						
Depressive state	PROMIS Emotional Distress - Depression 8b survey	CP, D		CP, D	CP, D*	CP, D
Depressive state	Patient Health Questionnaire-8 depression scale	D			D	D
Participant Medications						
Assessment of prescriptions	Custom survey/EHR	AP, CP, D	AP		CP, D	
Assessment of filled prescriptions	Medicaid and Medicare billing records for 12 months prior to time 0 through 6 months after time 0		AP, CP, D			

Adherence	Voils Medication Adherence		D		D	D	D
SSRI AE Survey	Custom survey		D		D	D	D
Opioid side effect survey	Adapted medication side effect survey (SPACE)		AP, CP	AP	AP, CP	AP, CP	AP, CP
Opioid persistence	Custom survey						AP
Participant Actions							
Interaction with provider	Participant visits				CP, D		
Interaction with test result	Custom survey						AP, CP, D
Quality of life and well being							
Past Medical History	Participant visits/custom survey		AP, CP, D				
Well-being	PROMIS43/PROMIS Peds37		AP, CP, D		AP, CP, D	AP, CP, D	AP, CP, D
Healthcare Utilization and Costs							
Medicare/Medicaid billing records	Medicaid and Medicare billing records for 12 months prior to time 0 through 6 months after time 0				AP, CP, D		
LoS	LoS for index admission			AP			
ED/urgent care & inpatient visits	Participant reported visits				AP, CP, D	AP, CP, D	AP, CP, D
Outpatient visits	Participant reported primary care & pain clinic visits				AP, CP, D	AP, CP, D	AP, CP, D
Outpatient visits	Long-term care or in-patient rehab days, home healthcare days				AP	AP	AP
Productively Loss	Survey of lost work time and income				AP, CP, D	AP, CP, D	AP, CP, D

Abbreviations: CP – chronic pain, AP – acute post-surgical pain, D-depression, ED – emergency department, EHR – electronic health record; LoS – length of stay; PT – physical therapy

\*Denote primary endpoints

## **8. SAFETY ASSESSMENT AND MONITORING**

ADOPT PGx is a prospective, multicenter, subset analysis of 1:1 randomized Intervention (immediate PGx testing and genotype-guided opioid or SSRI therapy with clinical decision support) vs. Control (usual care with delayed PGx testing) pragmatic, open label clinical trial. It is regulated under an Abbreviated Investigational Device Exemption (IDE). The genotyping-guided therapy is the device and classified as a minimal risk to the welfare of the enrolled participants. Only Adverse Device Effect (ADE) events suspected to be related to the specimen collection, laboratory assay genotyping results, and phenoconversion recommendations from the Best Practice Alerts (BPAs)/Consult notes will be reported to the IRB. Reportable ADEs or unanticipated Adverse Device Effect (UADEs) events including unanticipated study related deaths will be collected in the study database per IRB reporting policies. See the MOP for more details.

The IRB reporting timeline requirements are:

- Immediately (within 24 hours) upon learning of an unanticipated study-related death. Study personnel will notify the IRB via phone or email by providing a brief summary of the event; then within 1 week (5 business days), study personnel should submit report to IRB
- Within 5 business days for unanticipated events
- Within 10 business days for any other problem or event

### **8.1 Medication Side Effects**

Participant reported medication side effects will be collected in the baseline and follow-up surveys. The opioid medication side effects that will be surveyed include: problems with sleep; nausea, gas or indigestion; constipation or diarrhea; and dizziness or balance problems. The SSRI medication side effects that will be surveyed include: fatigue, change in weight, GI upset, sedation/somnolence, anxiety, insomnia, irritability/hostility, and sexual dysfunction.

### **8.2 Events of Interest**

Participant reported emergency department visits and hospitalizations will be collected in the 1, 3, and 6-month follow-up participant surveys. EHR may be used as an additional source for emergency department visits and hospitalizations, up to approximately 12 months after the last patient is randomized, i.e. through completion of the 6 month-follow up activities. For the details of collecting EHR data, see Protocol section 7.8 and MOP. EHR results will be sent to the CC via secure data transfer and formatted for data analyses.

### **8.3 Data Safety Monitoring Board**

The DSMB, appointed by the NHGRI, will be responsible for providing recommendations regarding the conduct of the study and guidance to ensure the safety and well-being of participants. The DSMB will meet semi-annually. A DSMB Charter will be developed detailing the procedures to be followed. A Data and Safety Monitoring Plan and a separate DSMB statistical analysis plan (SAP) will be developed in collaboration with the IGNITE PTN, IGNITE PTN CC, and NHGRI, and enacted by the DSMB.

### **8.4 Early Termination and Participant Discontinuation**

Early termination considerations will generally apply only to emerging issues of major concern, or problems with trial conduct that suggest the trial could not be completed successfully with a reliable conclusion in a feasible time frame.

The site investigator, sponsor or institution may stop involvement of any participant in this research

study at any time without their consent. This may be because the research study is being stopped, the instructions of the study team have not been followed, the investigator believes it is in the participant's best interest, or for any other reason. If specimens or data have been stored as part of the research study, they too may be destroyed without participant consent.

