#### **4.2 Blinding**

ADOPT PGx randomization assignments will not be blinded to the participants or their providers but will be masked to the UF call center personnel who may be administering some of the participants follow-up surveys. Due to the nature of the intervention, it is impossible to completely mask participants and providers from the pharmacogenetic testing and return of results, hence participants, providers, and local study personnel will not be blinded. While the UF call center personnel administering follow-up surveys will be masked from the results and randomization, study-arm specific questions in the final (6 month) survey may reveal study arm randomization. Additionally, participants may volunteer to reveal their randomization or PGx testing results. If the randomization or phenotype is revealed to the call center, prior to administering the 6 month surveys, it will be documented in the database.

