### **6.3 Participant Discontinuation/Withdrawal from the Study**

Participants may stop participating and withdraw from the study at any time. All information and data collected up until that point will be used in the study.

If a participant wishes to withdraw consent, they should contact study staff. A participant may also revoke HIPAA authorization and must provide the revocation in writing. Study staff may attempt to obtain a reason for withdrawal from the participant and record it in the study database.

In the acute pain trial, the principal investigators or clinical site investigators may withdraw a participant from the study for any of these reasons:

- Participant does not have the surgery within 12 months of study enrollment
- Participant has the surgery at a healthcare system that is different from where the participant enrolled
- Participant's surgery is scheduled for a date after the close of the enrollment period for that clinical site
- Participant is unable to have the surgery for other medical reasons

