## 7.5 Specimen Transfer and Genetic Testing Procedures

All collected specimens will be clearly marked with two patient identifiers (CLIA requirement). Samples from the Intervention arm participants will be processed, using analytically validated PGx testing procedures (see Table 1 for gene and variant list). For Control arm samples, designated laboratories will either extract DNA after sample receipt, and store the DNA for later analysis or store the sample and extract DNA after the Control participant has completed the 6-month follow-up assessment. After the Control participant has completed the 6-month follow-up assessment, Control Arm samples will be processed using analytically validated procedures. Details of sample storage and transport will be presented in the MOP.

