### **10.4 Analysis of the Primary Endpoint**

#### Acute Pain

To determine the effect of genotype-guided drug therapy on pain control in acute pain participants, we will conduct a subset analysis comparing SIA scores at 10-days post-surgery in the Intervention group subset with CYP2D6 IM or PM phenotypes to the Control group subset with CYP2D6 IM or PM phenotypes. Participants that have other CYP2D6 phenotypes will not be included. The 10-day post-surgery SIA scores of the Intervention CYP2D6 IM/PM group will be compared to the 10-day post-surgery SIA scores of the Control CYP2D6 IM/PM group using a two-sided two-sample t-test or Mann Whitney test, as appropriate, with a type 1 error of 0.049. This primary analysis will be conducted as a modified intent-to-treat analysis, with participants analyzed and endpoints attributed according to the treatment arm to which the participants were randomized, regardless of subsequent crossover or post-randomization medical care.

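### Section 8.4 permits open-ended stopping and destruction of stored specimens; because only control samples stay ungenotyped for months, stopped controls can drop out of the primary analysis set

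*Combined protocol and SAP*

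**What the plan says.** - **Stopping (Section 8.4).** "The site investigator, sponsor or institution may stop involvement of any participant in this research" study, without the participant's agreement. The grounds include that "the instructions of the study team have not been followed" and that "the investigator believes it is in the participant's best interest, or for any other reason".
- **Destruction (Section 8.4).** "If specimens or data have been stored as part of the research study, they too may be destroyed without participant consent". The sentence sets no limit by arm, timing or reason, does not require genotyping first, and names nobody as the one who destroys.
- **Blinding (Section 4.2).** "hence participants, providers, and local study personnel will not be blinded".
- **Sample handling (Section 7.5).** Intervention samples are processed as part of the intervention; Section 7.3 takes one week as the average from collection to results. For controls, the laboratory either extracts and stores DNA, or may "store the sample and extract DNA after the Control participant has completed the 6-month follow-up assessment". In both cases testing follows the completed 6-month assessment, and Section 10.7 confirms that control phenotypes become known at about that time.
- **Primary set (Section 10.3).** In each trial it is the randomized participants with an actionable phenotype, by genotype or by pheno-conversion.
- **Self-withdrawal (Section 6.3).** For participants who withdraw themselves: "All information and data collected up until that point will be used in the study".
- **Attribution (Section 10.4).** Participants are analysed "according to the treatment arm to which the participants were randomized, regardless of subsequent crossover or post-randomization medical care".

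**The concern.** Membership of the primary set depends on a laboratory result that exists early in one arm and late in the other. The primary endpoint falls at 10 days (acute pain) or 3 months (chronic pain, depression), while the control phenotype arrives at about 6 months. In acute pain the wait can be longer. Follow-up starts at surgery, and Section 6.3 makes the absence of surgery within 12 months a reason for withdrawal, so a control sample could stay ungenotyped for up to about 12 + 6 = 18 months.

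During that window, personnel who know the arm may stop a control on open grounds, and the specimen may then be destroyed. A comparable intervention participant usually already has a recorded phenotype and stays in the primary set. If the controls lost this way differ in outcome from those who remain, the randomized comparison is disturbed by a post-randomization exclusion that acts mainly on one arm. A destroyed specimen cannot be recovered by any later analysis. Section 10.8 imputes missing values but does not say what happens when the phenotype itself is missing. Section 10.1 says the actionable subgroup cannot be monitored directly, so such losses would be hard to see during the trial.

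**Working it through.** **1. The plan's own figures.** Inputs from Section 10.1 and Table 9: two-sided alpha 0.049, power 90%, standardized effects 0.375 (acute pain), 0.40 (chronic pain) and 0.28 (depression). An exact two-sample t-test calculation gives 151.2, 133.0 and 270.4 per arm. Rounded up, these are 152, 134 and 271, as in Table 9. The sample sizes are not in question.

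**2. What happens to set membership, by arm.**

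| Event after stopping | Intervention | Control |
|---|---|---|
| Specimen destroyed after the primary endpoint but before 6 months | Phenotype already in the study database (Section 7.6); stays classifiable | No genotype; unclassifiable unless on a strong CYP2D6 inhibitor |
| Specimen kept, 6-month assessment not completed | Already genotyped | No stated route to genotyping (Section 7.5) |
| Data destroyed | Lost | Lost |

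The asymmetry is in the first two rows. The second needs no destruction at all.

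**3. Controls who remain classifiable.** Section 7.1 treats anyone on a strong CYP2D6 inhibitor as a poor metabolizer, which needs no genotype; a moderate inhibitor halves the activity score, so a genotype is still needed. For chronic pain, Section 10.1 expects 10–15% actionable by genotype plus 20% by drug interaction. At most 20/35 = 57% to 20/30 = 67% of actionable participants there could be classified without a specimen. The true share is lower if some of the 20% are on moderate inhibitors; the documents do not give the split.

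**4. Size of a selective loss.** Let q be the fraction of actionable controls lost, and k the distance in SD between their mean and the mean of all actionable controls. The remaining control mean moves by q·k/(1 − q). The documents give neither q nor k. Assume k = 0.5 and q = 5% or 10%, with no loss in the intervention arm.

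| q | Shift (SD) | % of 0.375 (acute) | % of 0.40 (chronic) | % of 0.28 (depression) |
|---|---|---|---|---|
| 5% | 0.05 × 0.5 / 0.95 = 0.026 | 7.0 | 6.6 | 9.4 |
| 10% | 0.10 × 0.5 / 0.90 = 0.056 | 14.8 | 13.9 | 19.8 |

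If the lost controls did worse than average, the remaining control arm looks better and the apparent benefit shrinks; if they did better, it grows. By normal approximation, with no true effect, the nominal 0.049 two-sided rejection rate becomes 0.055 (acute pain) and 0.059 (depression) at q = 5%, and 0.075 and 0.095 at q = 10%.

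**5. Power.** With the same one-arm losses and no selection, power in acute pain, chronic pain and depression is 0.894, 0.895 and 0.893 at 5%, against a planned 0.90. Loss of numbers matters little; selective loss is the issue.

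**6. What the assumption implies.** Phenotype is unknown when a control is stopped, so losing 5% of 152 actionable acute pain controls (7.6, about 8) implies losing about 0.05 × 845 = 42 controls of all phenotypes. The 10% case implies about 85.

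**The case against.** Several objections are sound and limit the point.

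- **Destroyed specimens and classification.** A reader might infer that a control whose specimen is destroyed can never be classified. The strong-inhibitor rule shows otherwise, and baseline medications are collected (Section 7.2).
- **Contradiction with Sections 6.3 and 10.4.** A reader might infer that 8.4 contradicts both. The retention sentence in 6.3 concerns participants who withdraw themselves, whereas 8.4 concerns stops by others. Section 10.4 says to which arm endpoints are attributed and is silent on keeping specimens or data. These are rules to align, not direct contradictions.
- **Who destroys.** A reader might infer that an unblinded investigator may personally destroy material. Section 8.4 names no one; designated laboratories hold control samples and the coordinating center maintains the database.
- **Both arms.** Destroying data affects both arms, and intervention samples are also ungenotyped for about a week.
- **Mechanism.** Poor symptom control is not a listed ground. Phenotype is unknown at the decision, so actionable controls cannot be targeted. Follow-up surveys may come through a masked call center. Controls receive usual care, so their study instructions are largely survey completion, and someone stopped for ignoring them may lack the endpoint anyway.
- **Size.** The 5–10% and 0.5 SD are assumptions. The 10% case equals the whole planned drop-out allowance, all in one arm.
- **Other documents.** Storage details are left to the Manual of Operations and further missing-data rules to a separate SAP.

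What stands is that the protocol text leaves the permission open-ended, gives controls stopped before 6 months no route to genotyping, and exposes the two arms unequally on the specimen side.

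**Conclusion.** The point holds as a risk of differential post-randomization exclusion from the primary set. It is not a demonstrated bias: 8.4 is a permission, and nothing in the documents says how often it would be used. The exposed group is stopped controls who need a genotype for classification, that is, actionable controls not taking a strong CYP2D6 inhibitor.

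Under the stated assumptions the contrast would move by 0.026 to 0.056 SD. That is modest against the design effects and could go either way, so a reader should not infer that it favours the intervention. The case for acting rests less on expected size than on irreversibility and on how little the change costs.

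**What to change.** - **Section 8.4.** Replace the destruction sentence with a retention rule. When a site, the sponsor or an institution stops a participant, data and specimens already collected are kept and used. The stored specimen is genotyped for analysis-set classification in either arm, whether or not the 6-month assessment was completed. Exceptions: the participant asks for destruction, consent or assent is invalid, or the IRB directs destruction.
- **Section 8.4.** State that not following study-team instructions does not remove a randomized participant from the analysis.
- **Sections 6.3 and 7.5.** Align them with this rule, so that 6.3 also covers stops initiated by others and 7.5 gives a genotyping route for controls who stop before 6 months.

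The cost is protocol and consent wording, genotyping of a few extra stored samples, and loss of a discretionary power that the analysis plan does not need.

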## 9. MEDICARE AND MEDICAID CLAIMS DATA COLLECTION AND ANALYSIS

### 9.1 Rationale

The economic analyses will be conducted from the perspective of the payer with the primary goal to provide cost-effectiveness data that can inform reimbursement decisions for genotyping. Reporting metrics will include:

1. Average costs for each study arm, considering overall cost to the payer and select services directly relevant to the acute pain, chronic pain, and depression groups
2. Differences in cost utility between the intervention arm, considering overall cost to the payer and select services directly relevant to the acute pain, chronic pain, and depression groups
3. Incremental cost-effectiveness ratio (ICER), i.e., the incremental change in cost per unit improvement of effectiveness.

All metrics will be ascertained over a 6-month follow-up period with the assumption that beneficial effects of genotype-guided therapy are fully realized within this time period and that the control arm participants have not yet developed any cross-over effects from the 6-month delayed testing.

In a population of mixed payer types, collecting actual costs for all participants is not feasible. Therefore, costs will be obtained from Medicare and Medicaid claims data and imputed or cross-walked to the other payer types. Based on data in the National Inpatient Sample, 53% and 4% of knee and 59% and 4% of hip arthroplasties were reimbursed by Medicare and Medicaid, respectively. For chronic pain participants, data from the University of Florida suggest 40% and 20% are covered by Medicare and Medicaid, respectively. Thus, considering enrollment gaps, at least 60% of the study population is anticipated to have claims data, from which comprehensive cost analyses can be performed and extrapolated to the entire cohort. Major cost drivers associated with pain and depression will be ascertained from the participant using validated resource questionnaires, and verified through secondary claims data whenever possible.

